6.4.2. Additional considerations

The ANCOVA is used to adjust for the potential baseline imbalance between study groups. The ANCOVA analysis will be performed for the primary endpoint.

In addition, an Analysis of Variance (ANOVA) model with vaccine group and center (if applicable) as factors will be fitted in order to compute the estimates (not adjusted for pre-vaccination titer) together with their associated 95% CIs by exponentiating the corresponding log-transformed means and their 95% CIs.

205343 (MENACWY CONJ-032 [V59_71]) Statistical Analysis Plan Amendment 1 Final

For the 'by country' subgroup analysis, the ANCOVA and ANOVA models will be fitted without country in the model.

Given the high likelihood of having centers with few subjects enrolled in the study; therefore, country will be used as a factor in the ANCOVA/ANOVA analyses instead of center.

Permutation test (sensitivity analysis on primary objectives)

Based on the covariate-adaptive vaccine assignment algorithm (see Section 14 (Annex 4)), the following permutation test [Wiens, 2006; Hasegawa, 2009 and Ernst, 2004] will be performed as a sensitivity analysis on the primary objective in the PPS.

For serogroup A, let $\mathbf{X} = (X_1, ..., X_N)$ the logarithmically-transformed hSBA titers for the ACWY_liq group and $\mathbf{Y} = (\mathbf{Y}_1, ..., \mathbf{Y}_N)$ the logarithmically-transformed hSBA titers for ACWY group at 1 month after vaccination. A non-inferiority permutation test can be obtained from a superiority permutation test on $\dot{\mathbf{X}} = (X_1 + \delta, ..., X_N + \delta)$ against $\dot{\mathbf{Y}} = (\mathbf{Y}_1, ..., \mathbf{Y}_N)$ with $\delta = 0.301 = -\log_{10}(0.5)$.

The original vaccine assignment algorithm Section 14 (Annex 4) will be used to rerandomize subjects belonging to the ACWY_Liq group and ACWY group (see step 2a) while keeping hSBA titers, covariates and entry order as observed. The procedure will be as follows:

- 1. Fit the ANCOVA model to obtain the test statistics T^* for the superiority of \dot{X} against \dot{Y} ;
- 2. Estimate the distribution of the corresponding test statistic with R=10 000 repetitions of the following two steps:
 - a. Re-randomize vaccine assignment of groups $\dot{\mathbf{X}}$ and $\dot{\mathbf{Y}}$ (original algorithm);
 - b. Re-fit the full ANCOVA model to re-obtain the test statistics T;
- 3. Derive the permutation p-values associated with the observed test statistics (from Step 1) based on the empirical distributions in Step 2;

p-value = M+1/R+1, where M is the number of repetitions such that $T \ge T^*$.

6.5. Analysis of safety

6.5.1. Analysis of safety planned in the protocol

Safety analysis will be performed on the solicited safety set for solicited reactions and on unsolicited safety set for unsolicited adverse events.

Analysis of Solicited Local, Systemic and Other Adverse Events

All solicited adverse events will be summarized according to defined severity grading scales.

205343 (MENACWY CONJ-032 [V59_71]) Statistical Analysis Plan Amendment 1 Final

Frequencies and percentages of subjects experiencing each adverse event will be presented for each symptom severity. Summary tables showing the occurrence of any local or systemic adverse event overall and at each time point will also be presented.

Post-vaccination solicited adverse events reported from Day 1 to Day 7 will be summarized for the intervals Day 1 (6 hours) – Day 3, Days 4-7, Day 1 (6 hours) – Day 7 by maximal severity and by study group. Separate analyses will be performed for solicited AEs reported 30 minutes after vaccination. The severity of solicited local adverse events, including injection-site erythema and induration, will be categorized based on linear measurement: Absent < 25 mm, Mild (25-50 mm), Moderate (51-100 mm), Severe (> 100 mm).

Injection site pain and systemic reactions, including fatigue, headache, myalgia, arthralgia, chills, nausea, loss of appetite, occurring up to 7 days after each vaccination will be summarized according to "mild", "moderate" or "severe". The assessment of the intensity of solicited AEs is detailed in section 8.3.3.2.1 of the protocol.

Each solicited local and systemic adverse event will also be further summarized as "absent" versus "any".

Use of antipyretics and analgesics will be summarized by frequency, by type of use (prophylactic versus treatment) and percentage of subjects reporting use.

Body temperature will be summarized separately according to the 2 schemes described below and will be broken down according to route of measurements (axilla, oral cavity, rectum, tympanic membrane):

- by 1°C increments: <36.0, 36.0-36.9, 37.0-37.9, 38.0-38.9, 39.0-39.9, ≥40°C;
- According to different cut-offs (< versus ≥): 38.0, 38.5, 39.0, 39.5, 40.0°C.

Solicited AEs reported within 30 minutes post-vaccination will be summarized in a separate table.

Analysis of Unsolicited Adverse Events

This analysis applies to all adverse events occurring during the study, judged either as related or not related to vaccination by the investigator, recorded in AE CRF, with a start date on or after the date of first vaccination. AE starting prior to the first vaccination will only be listed. The original verbatim terms used by investigators to identify adverse events in the CRFs will be mapped to preferred terms using the MedDRA dictionary. The adverse events will then be grouped by MedDRA preferred terms into frequency tables per system organ class (SOC).

All reported adverse events, as well as adverse events judged by the investigator as at least related to study vaccine, will be summarized per SOC and preferred term within SOC. These summaries will be presented by study group and by interval of study observation (with onset from Day 1 through Day 29, during the follow-up period and throughout the study period). When an adverse event occurs more than once for a subject, the maximal severity and strongest relationship to the vaccine will be counted.

205343 (MENACWY CONJ-032 [V59_71]) Statistical Analysis Plan Amendment 1 Final

Separate summaries will be produced for the following categories:

- Adverse events that are related to vaccine
- Unsolicited AEs reported within 30 minutes after vaccination
- Unsolicited AEs reported within 29 days after vaccination
- Adverse events leading to withdrawal
- Adverse events leading to a medically attended visit
- Serious adverse events
- Adverse events leading to Death

Data listings of all adverse events will be provided by subject. In addition, adverse events in the categories above will be provided as listed data (excluding Unsolicited AEs reported within 29 days after vaccination).

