| Solicited adverse event: | AEs to be recorded as endpoints in the clinical study. The presence/occurrence/intensity of these events is actively solicited from the subject or an observer during a specified post-vaccination follow-up period. |
| Study vaccine/product: | Any investigational vaccine/product being tested and/or any authorized use of a vaccine/ product /placebo as a reference or administered concomitantly, in a clinical trial that evaluates the use of an investigational vaccine/product. |
| Sub-cohort: | A group of subjects for whom specific study procedures are planned as compared to other subjects or a group of subjects who share a common characteristic (e.g. ages, vaccination schedule,...) at the time of enrollment. |
| Subject: | Term used throughout the protocol to denote an individual who has been contacted in order to participate or participates in the clinical study, either as a recipient of the vaccines or as a control. |
| Subject number: | A unique number identifying a subject, assigned to each subject consenting to participate in the study. |
| Treatment: | Term used throughout the clinical study to denote a set of investigational product(s) or marketed product(s) or placebo intended to be administered to a subject. |
| Treatment number: | A unique number identifying a treatment to a subject, according to treatment allocation. |
| Unsolicited adverse event: | Any AE reported in addition to those solicited during the clinical study. Also any 'solicited' symptom with onset outside the specified period of follow-up for solicited symptoms will be reported as an unsolicited adverse event. |

TRADEMARKS

The following trademarks are used in the present protocol.

Note: In the body of the protocol (including the synopsis), the names of the vaccines will be written in *italics*.

| Trademarks of the GSK group of companies | Generic description |
|---|---|
| Menveo | Meningococcal (Serogroups A, C, Y, and W-135) oligosaccharide diphtheria CRM ₁₉₇ conjugate vaccine |
| Trademarks not owned by the GSK group of companies | Generic description |
| Nimenrix (Pfizer, Inc.) | Meningococcal (Serogroups A, C, Y, and W-135) oligosaccharide tetanus toxoid conjugate vaccine |

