8.1. Safety definitions

8.1.1. Definition of an adverse event

An AE is any untoward medical occurrence in a clinical investigation subject, temporally associated with the use of a medicinal product, whether or not considered related to the medicinal product.

An AE can therefore be any unfavourable and unintended sign (including an abnormal laboratory finding), symptom, or disease (new or exacerbated) temporally associated with the use of a medicinal product. For marketed medicinal products, this also includes failure to produce expected benefits (i.e. lack of efficacy), abuse or misuse.

Examples of an AE include:

- Exacerbation of a chronic or intermittent pre-existing condition including either an increase in frequency and/or intensity of the condition.
- New conditions detected or diagnosed after study vaccines administration even though they may have been present prior to the start of the study.
- Signs, symptoms, or the clinical sequelae of a suspected interaction.
- Signs, symptoms, or the clinical sequelae of a suspected overdose of either study vaccines or a concurrent medication (overdose per se should not be reported as an AE/SAE).
- Signs, symptoms temporally associated with study vaccines.
- Significant failure of expected pharmacological or biological action.
- Pre- or post-treatment events that occur as a result of protocol-mandated procedures (i.e. invasive procedures, modification of subject's previous therapeutic regimen).

AEs to be recorded as endpoints (solicited AEs) are described in Section 8.1.3. All other AEs will be recorded as UNSOLICITED AEs.

Examples of an AE DO NOT include:

- Medical or surgical procedures (e.g. endoscopy, appendectomy); the condition that leads to the procedure is an AE/SAE.
- Situations where an untoward medical occurrence did not occur (e.g. social and/or convenience admission to a hospital, admission for routine examination).
- Anticipated day-to-day fluctuations of pre-existing disease(s) or condition(s) present or detected at the start of the study that do not worsen.
- Pre-existing conditions or signs and/or symptoms present in a subject prior to the study vaccination. These events will be recorded in the medical history section of the eCRF.

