8.1.3.3. Other Solicited Adverse Events

Other indicators of reactogenicity:

- Use of analgesics / antipyretics for treatment;
- Use of analgesics / antipyretics for prophylaxis;

The study staff must review the data entered into the Subject Diary as described in Section [11.2](#).

Note: Any solicited adverse event that meets any of the following criteria must be entered into subjects' source document (see Section [11.2](#)) and also as an adverse event on the Adverse Event CRF:

- Solicited local or systemic adverse event that leads to a visit to a healthcare provider (medically attended adverse event, see Section [8.3.3.4](#)).
- Solicited local or systemic adverse event leading to the subject withdrawing from the study or the subject being withdrawn from the study by the investigator (adverse event leading to withdrawal).
- Solicited local or systemic adverse event that otherwise meets the definition of a serious adverse event (see Section [8.1.2](#)).

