8.1.4. Unsolicited Adverse Events

An unsolicited adverse event is an adverse event that was not solicited using a Subject Diary and that was spontaneously communicated by a subject/parent(s)/LAR(s) who has signed the informed consent.

Potential unsolicited AEs may be medically attended (defined as symptoms or illnesses requiring hospitalization, or emergency room visit, or visit to/by a health care provider), or were of concern to the subjects/parents/LARs. In case of such events, subjects/parents/LARs will be instructed to contact the site as soon as possible to report the event(s). The detailed information about the reported unsolicited AEs will be collected by the qualified site personnel during the interview and will be documented in the subject's records.

Unsolicited AEs that are not medically attended nor perceived as a concern by subjects/parents/LARs will be collected during interview with the subjects/parents/LARs and by review of available medical records at the next visit.

8.1.5. Clinical laboratory parameters and other abnormal assessments qualifying as adverse events or serious adverse events

In absence of diagnosis, abnormal laboratory findings (e.g. clinical chemistry, haematology, urinalysis) or other abnormal assessments (e.g. clinical signs, ECG, radiological or diagnostic assessments) that are judged by the investigator to be clinically significant will be recorded as AE or SAE if they meet the definition of an AE or SAE (refer to Sections 8.1.1 and 8.1.2). Clinically significant abnormal laboratory findings or other abnormal assessments that are present at baseline and significantly worsen following the start of the study will also be reported as AEs or SAEs. However, clinically significant abnormal laboratory findings or other abnormal assessments that are present or detected at the start of the study and do not worsen, will not be reported as AEs or SAEs.

The investigator will exercise his or her medical and scientific judgement in deciding whether an abnormal laboratory finding or other abnormal assessment is clinically significant.

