8.3.3.2.2. Assessment of causality

The investigator is obligated to assess the relationship between study vaccines and the occurrence of each AE/SAE using clinical judgement. In case of concomitant administration of multiple vaccines/products, if possible, the investigator should specify if the AE could be causally related to a specific vaccine/product administered (i.e. investigational, control/placebo or co-administered vaccine). When causal relationship to a specific vaccine(s)/product(s) cannot be determined the investigator should indicate the AE to be related to all products.

Alternative plausible causes, such as natural history of the underlying diseases, concomitant therapy, other risk factors, and the temporal relationship of the event to the study vaccines will be considered and investigated. The investigator will also consult the IB and/or SmPC and/or Prescribing Information for marketed products to determine his/her assessment.

There may be situations when a SAE has occurred and the investigator has minimal information to include in the initial report to GSK Biologicals. However, it is very important that the investigator always makes an assessment of causality for every event prior to submission of the Expedited Adverse Events Report to GSK Biologicals. The investigator may change his/her opinion of causality in light of follow-up information and update the SAE information accordingly. The causality assessment is one of the criteria used when determining regulatory reporting requirements.

All solicited reactions will be considered causally related to vaccination. Causality of all other AEs should be assessed by the investigator using the following question:

Is there a reasonable possibility that the AE may have been caused by the study vaccine?

- YES : There is a reasonable possibility that the study vaccine contributed to the AE.
- NO : There is no reasonable possibility that the AE is causally related to the administration of the study vaccine. There are other, more likely causes and administration of the study vaccine is not suspected to have contributed to the AE.

If an event meets the criteria to be determined as ‘serious’ (see Section 8.1.2), additional examinations/tests will be performed by the investigator in order to determine ALL possible contributing factors for each SAE.

Possible contributing factors include:

- Medical history.
- Other medication.
- Protocol required procedure.

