11.2. Subject Diary

Electronic Diaries (eDiaries), hereafter referred to as Subject Diaries will be the only source document allowed for solicited local and systemic adverse events (including body temperature measurements), starting after the initial 30 minute post-vaccination period at the clinic. The following additional rules apply to documentation of safety information collected in the Subject Diary.

The Investigator or delegated staff should monitor the Subject's Diary status throughout the study for compliance and any solicited local and systemic adverse events that were of concern to the subject.

- No corrections or additions of data recorded by the subjects/parents/LARs will be allowed once diary completion for that day has been performed.
- The Subject Diary will be designed in such a way as to prevent any blank, incomplete or biologically implausible entries. Subjects/parents/LARs will be instructed to fully complete the Subject Diary each day, as per the instructions provided.

- At or just in advance of each subject visit, site staff must review the Subject Diary data via the provider's web portal. It is necessary for site staff to acknowledge in the source documents that review of Subject Diary data for the preceding post-vaccination period has been performed. At the end of the study it is necessary for the investigator to acknowledge in the eCRF that the review of Subject Diary data has been performed for each subject.
- For vaccination visits, site staff must ensure that each subject's Diary is prepared for data capture in the ensuing post-vaccination period by confirming the visit within the eDiary/eDiary system.
- Any new safety information reported during the site visit (including a solicited adverse event) cannot be entered into the Subject Diary. Such information must be described in the source notes as a verbally-reported event. Any adverse event reported in this fashion must be described as an unsolicited adverse event and therefore entered on the adverse event page of the eCRF.

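### Solicited reactions that also go on the AE CRF will appear in the general unsolicited AE tables, because the SAP selects unsolicited AEs by form and has no rule to remove them

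*SAP*

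**What the plan says.** **Selection rule.** SAP 6.5.1, repeating protocol 10.8.2, takes as its scope all AEs "recorded in AE CRF, with a start date on or after the date of first vaccination". SAP 6.5.2.3 adds only that the event must be vaccine-emergent and is assigned to an interval by day of onset. Neither section mentions solicited terms.

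**What goes on the form.** Under protocol 8.1.3.3, a solicited local or systemic reaction that leads to a healthcare visit, leads to withdrawal or is serious is put in the source document "and also as an adverse event on the Adverse Event CRF". The diary record remains, because protocol 11.2 allows no correction once a day's entry is complete.

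**Definitions.** Protocol 8.1.1 points to the solicited list and then states "All other AEs will be recorded as UNSOLICITED AEs". Protocol 8.1.4 says "An unsolicited adverse event is an adverse event that was not solicited using a Subject Diary". The glossary adds that a solicited "symptom with onset outside the specified period of follow-up for solicited symptoms will be reported as an unsolicited adverse event".

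**Verbal reports.** Protocol 11.2 says "Any new safety information reported during the site visit (including a solicited adverse event) cannot be entered into the Subject Diary", and then "Any adverse event reported in this fashion must be described as an unsolicited adverse event".

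**Causality.** Protocol 8.3.3.2.2 says "All solicited reactions will be considered causally related to vaccination". All other AEs are left to the investigator's judgement.

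**The concern.** The analysis is defined by the form an event sits on, while the protocol's definitions turn on what the event is and how it was collected. The two agree only if no solicited reaction reaches the AE CRF, and protocol 8.1.3.3 guarantees that some will. A Day 2 headache entered in the diary that leads to a doctor's visit is a solicited headache in one set of tables and an unsolicited AE in another. It is related by rule in the first and carries an investigator's causality judgement in the second.

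Solicited AEs from 6 hours to Day 7 and unsolicited AEs from Day 1 to Day 29 are separate named secondary safety endpoints. A reader comparing them will take the second to be additional to the first. If diary reactions are mixed in, the unsolicited rate is overstated as an absolute figure.

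**Working it through.** The plan states no figure on this point, so the check is mainly a reading of the rules, followed by a scale calculation.

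**Step 1: test each route onto the AE CRF against the definitions, for onset within the solicited period.**

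| Route | 8.1.1 (not on solicited list) | 8.1.4 (not solicited by diary) | Glossary (onset outside period) | 11.2 |
|---|---|---|---|---|
| In the diary and also on the AE CRF (8.1.3.3) | not unsolicited | not unsolicited | not unsolicited | silent |
| Told to the site only, no diary entry | not unsolicited, if read by symptom | unsolicited | not made unsolicited by the onset clause | unsolicited, explicitly |

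The first route fails all three definitions, and nothing else in the documents admits it. The second is settled by the specific rule in protocol 11.2 and fits 8.1.4.

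**Step 2: which outputs are affected.** Dual-entered reactions enter the all-reported, related and 29-day unsolicited tables. Their presence in the medically attended, withdrawal, SAE and death summaries is appropriate. Within one unsolicited table, SAP 11.2 counts a subject once per preferred term. The combined table in SAP 6.5.2.4 pools both sources for non-serious events. It would show a dual-entered event twice if events rather than subjects are counted, and the SAP gives no rule.

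**Step 3: scale on the unsolicited side.** Input: 486 planned per group (protocol 10.3); the actual safety-set denominators will differ.

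- Per affected subject: 1/486 = 0.206%, or 0.21 points.
- The fraction m with a dual-entered reaction is not in the documents. Assume 2%, range 1-4%: 0.02 × 486 = 9.7 subjects (4.9 to 19.4).
- Upper bound, if none of them has another unsolicited AE: 2 points (1 to 4).
- Allowing for overlap, with true unsolicited rate U and independence, the reported rate is 1 − (1 − U)(1 − m).
 - U = 20% (assumed): m = 1%, 2%, 4% gives 20.8%, 21.6%, 23.2%.
 - U = 30% (assumed): 30.7%, 31.4%, 32.8%.

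**Step 4: the solicited side, for verbal-only reports.** Under SAP 6.5.2.2 a subject with at least one plausible diary value for the event in the interval stays in the denominator, and is 'none' unless something above 'absent' was reported. A subject with no plausible value is dropped. Let T be the true rate of any systemic reaction (assumed 50%) and v the fraction whose only positive report was verbal.

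- All have a partial diary: T − v. For v = 1%, 3%, 5%: 49.0%, 47.0%, 45.0%.
- All have no diary data in the interval: (T − v)/(1 − v). For the same v: 49.5%, 48.5%, 47.4%.

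**The case against.** The best answer is that the section heading and the 29-day category both say unsolicited, a defined term, so a careful programmer would filter. The table shells, which are outside the documents, may do so. That is possible, but the only operational rule written down is the scope sentence, and it selects by form. Subject listings and the separate medically attended, withdrawal and SAE tables keep the events visible, but they do not correct the general incidence tables.

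Three stronger readings are tempting, and the documents do not support them.

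- *Reactions are double-counted within a table.* An event appears once in each of two outputs that the plan never adds together, and a subject counts once per preferred term. Only the combined registry table is exposed, and only if it counts events.
- *Verbally reported reactions are misclassified.* Protocol 11.2 deliberately makes them unsolicited, and 8.1.4 admits them. Moving them out of the unsolicited tables would contradict the protocol and could leave some in neither main table. Calling them related by rule would override the investigator assessment that 8.3.3.2.2 asks for.
- *Every reaction missed in the diary becomes 'none'.* This holds only where the subject has other plausible diary data for that event in the interval. Otherwise the subject leaves the denominator, and a missed day drops out of the daily table. Daily alarms and non-compliance alerts to sites (protocol 5.6.14.1.1) also limit missed entries.

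What remains of the verbal-report issue is narrower. With a partial diary, a positive report held in the trial database is shown as 'none', the downward bias that SAP 6.5.2.2 sets out to prevent for subjects with no data.

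**Conclusion.** The point holds for dual-entered reactions. As written, SAP 6.5.1 brings them into the general unsolicited, related and 29-day tables against every definition the protocol gives, and SAP 6.5.2.4 has no rule for an event in both sources.

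The size is 0.21 points per affected subject at most. On an assumed 1-4% of subjects it is at most about 1 to 4 points, and less with overlap. Those percentages are illustrations, since the documents give no rate.

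A reader might infer that the group comparison or the trial's conclusion is at risk. The documents do not support that. SAP 6.5.2 plans no statistical comparison of safety between groups, the same collection rules apply to both groups so the effect is probably similar, and the primary endpoint is an hSBA titer. The issue is the accuracy of absolute descriptive rates. It is worth correcting because the correction is cheap.

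One route is undetermined: the documents do not say whether solicited events from the 30-minute assessment, which are entered in the eCRF, sit on its AE page.

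**What to change.** In SAP 6.5.1 and 11.2, define a flag for AE CRF records that meet all three conditions: the term matches a solicited symptom, using the coding list already in SAP 6.5.2.4; onset is within the solicited period; and the subject has a matching diary entry. Then:

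1. Exclude flagged records from the general unsolicited, related and 29-day incidence tables.
2. Keep them in the medically attended, withdrawal, SAE and death tables and in the listings.
3. In the combined table of SAP 6.5.2.4, count each such event once per subject.
4. Leave solicited reactions reported only verbally as unsolicited, as protocol 11.2 requires, with the investigator's causality unchanged.
5. Add one supplementary 6-hour-to-Day-7 solicited summary in which verbal-only reports with onset in that window count as 'any'. The main solicited tables stay as planned.

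The cost is some SAP wording, one derived flag and one extra table, with no new data and no change to the protocol. The limitation to footnote is that verbal reports lack diary confirmation, which is why they belong in a supplementary summary.
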